4.1 Overall Design

This is a phase 1b study assessing safety, tolerability, PK, pharmacodynamics, and efficacy of AMG 330 administered as clV infusion in combination with pembrolizumab in adult subjects with R/R AML.

The study is a non-randomized study and will consist of 2 sequential dosing cohorts. Both cohorts will include AMG 330 and pembrolizumab with the difference being the initiation date for pembrolizumab treatment.

This study will use a staggered enrollment approach. Subject enrollment will start with cohort 1 ([Section 4.1.1](#)). The first subject dosed in cohort 1 will serve as the sentinel subject. Subsequent subjects dosed in cohort 1 will start AMG 330 (█ µg/day) administration once sentinel subject has cleared the study day 21 dose (AMG 330 monotherapy at █ µg/day). Per sponsor determination, if the sentinel subject does not experience a dose-limiting toxicity (DLT) on days 15 to 21 after pembrolizumab is administered, the other subjects in cohort 1 will be allowed to continue the planned treatment schedule. If the sentinel subject experiences a DLT during days 15 to 21, the dose level review team (DLRT) will discuss the case and the decision will be made by the sponsor based on clinical assessments of the adverse event and potential decisions by the sponsor may include stopping AMG 330 and/or pembrolizumab, dose de-escalation of AMG 330, or continuing therapy at full dose. Investigators and sponsor will meet after all subjects in cohort 1 have completed study day 28 (ie, AMG 330 █ µg/day dose level in combination with pembrolizumab) to assess the safety profile. If pre-specified safety criteria are met (≤ 3 out of 10 treated subjects in cohort 1 experienced DLT by day 28), subjects enrolled in cohort 2 ([Section 4.1.2](#)) may proceed with the treatment schedule. Similar to cohort 1, the first subject dosed in cohort 2 will serve as the sentinel subject. Per sponsor determination, if the sentinel subject does not

experience a DLT during the first 7 days, the other subjects in cohort 2 will be allowed to continue the planned treatment schedule.

Safety data will be continuously monitored throughout the whole treatment period. Sponsor in consultation with investigators may reconvene to make appropriate safety measures and adjustments as needed.

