6.2 Dose Modification

6.2.1 Dose-cohort Study Escalation/De-escalation and Stopping Rules, Dose-Limiting Toxicities (DLTs)

Step Dose Level Determination

A decision to proceed with the next step dose of AMG 330 for each subject in cohorts 1 and 2 will be based on investigator's assessment of safety and upon approval by Sponsor.

In cohort 1, a sentinel subject will be treated first. The minimal interval between treatment start for the sentinel subject and other subjects in the cohort is 21 days. If the sentinel subject has not experienced a DLT by day 14 at █ µg/day AMG 330, he/she will proceed with 200 mg pembrolizumab on day 15 and remain at an AMG 330 dose level of █ µg/day for 7 days (until day 21). If the sentinel subject experiences a DLT during the first 7 days of treatment with AMG 330 at █ µg/day, this subject will be replaced, but the DLT will still be counted towards the study stopping rules. If the sentinel subject does not experience a DLT before or on day 21, the next subjects in the cohort may initiate dosing. If a sentinel subject experiences a DLT, the sponsor will issue a decision based on the evaluation of clinical significance of the adverse event by the DLRT and potential decisions by the sponsor may include stopping AMG 330 and/or pembrolizumab, dose de-escalation of AMG 330, or continuing therapy at full dose.

Cohort 2 will be initiated only after all subjects in cohort 1 completed study day 28 (ie, AMG 330 █ µg/day dose level in combination with pembrolizumab for 7 days), and if the rate of DLT is ≤ 3 out of 10 subjects. After receiving the DLRT recommendation, sponsor will render a final decision and will issue a written notification of the decision to investigators. Further information on dose level review meetings (DLRMs) is provided in [Section 11.3](#).

Individual Stopping Rules

Dosing for an individual will be stopped for any occurrence of a DLT. The event will be reviewed by the investigator and Sponsor for evidence of relationship to treatment and

clinical or medical significance to decide whether dosing may be resumed for the individual and any modifications to the dosing, if appropriate.

Dose Limiting Toxicities

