9.4.1 Planned Analyses

9.4.1.1 Interim Analysis and Early Stopping Guidelines

Safety data will be reviewed on an ongoing basis. A DLRM will occur when at least 10 treated subjects in cohort 1 have been dosed through study day 28 to determine if the safety profile of initial steps in cohort 1 is acceptable to begin enrollment of cohort 2 or if the study should be stopped. If 3 or more of the 10 treated subjects in cohort 1 experience a DLT by day 28, the guidance to the DLRT is to recommend not to initiate cohort 2. The stopping rule is based on having at least a posterior probability of > 70% that the DLT rate is > 20% assuming a prior distribution of Beta (0.40, 1.60). If the true DLT rate is 10%, 20%, 30%, 40%, or 50%, then the probability of stopping the study at the interim analysis is 7%, 32%, 62%, 83%, 95%, respectively.

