11.3 Appendix 3. Study Governance Considerations

Dose Level Review Meetings

In this study, a dose level review meeting (DLRM) will be conducted 1 time to review and interpret safety data for the purposes of making recommendations about opening cohort 2 and evaluating safety signals for purposes of applying dose cohort/individual stopping rules. The Dose Level Review Team (DLRT) will meet to confirm the decision rules when the following criterion is met:

- at least 10 treated subjects in cohort 1 have been dosed through the end of [REDACTED] µg/day Step Dose (study day 28).

The required DLRT members are the Early Development Lead, Medical Monitor, Global Safety Officer (GSO), and Site Investigators. The DLRT will also include the Early Development Medical Director (Merck) in an advisory role. The DLRT will include Site Investigators from activated sites. The Early Development Lead, Medical Monitor, GSO, and Site Investigators are the only voting DLRT members. The following non-voting Amgen representatives may also be part of the DLRT: clinical study manager, biostatistician, pharmacokinetics (PK) scientist.

The Early Development Lead and Medical Monitor must be in attendance and cannot be represented by a voting designee or delegate. Voting designees can be identified as appropriate by the GSO or Site Investigator(s). A Site Investigator may identify a delegate (eg, sub-Investigator) who is listed in the Delegation of Authority. If a Site Investigator does this, the Site Investigator must provide written agreement with the designee or delegate's vote.

For a DLRM to occur, the Early Development Lead and Medical Monitor must attend, and the GSO or delegate must attend. In addition, a quorum of Site Investigators must be present. A quorum is defined as more than 50% of the participating investigators or their qualified designee. The DLRM will be rescheduled if these requirements are not met.

All available study data, including demographics, investigational product administration, medical history, concomitant medications, adverse events, electrocardiogram (ECG), vital signs, and laboratory results will be reviewed. Data to be reviewed will be unqueried.

DLRM voting will occur as follows: there will be a total of 4 votes, 1 for Early Development Lead, 1 for the Medical Monitor, 1 for the GSO or delegate, and 1 for all of

Approved

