### 7. Planned Analyses

# 7.1 Interim Analysis and Early Stopping Guidelines

Safety data will be reviewed on an ongoing basis. The dose level review meeting (DLRM) will occur when at least 10 treated subjects in cohort 1 have been dosed through study day 28 to determine if the safety profile of initial steps in cohort 1 is acceptable to begin enrollment of cohort 2 or if the study should be stopped. If 3 or more of the 10 treated subjects in cohort 1 experience a DLT by day 28, the guidance to the DLRT is to recommend not to initiate cohort 2. The stopping rule is based on having at least a posterior probability of > 70% that the DLT rate is > 20% assuming a prior distribution of Beta (0.40, 1.60). If the true DLT rate is 10%, 20%, 30%, 40%, or 50%,

Protocol Number: 20170646

Date: 25 August 2020 Page 18 of 35

then the probability of stopping the study at the interim analysis is 7%, 32%, 62%, 83%, 95%, respectively.

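### After the one scheduled cohort 1 day-28 review, no number of DLTs requires a hold on new starts or a further review-team meeting; and the day-28 threshold itself is written two ways

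*Protocol*

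**What the plan says.** Protocol Section 11.3 provides for one scheduled meeting: "a dose level review meeting (DLRM) will be conducted 1 time to review and interpret safety data". Its purposes are to recommend whether to open cohort 2 and "evaluating safety signals for purposes of applying dose cohort/individual stopping rules". It reviews all available study data, and a recommendation to open cohort 2 must be unanimous.

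The only DLT count across subjects is in protocol 9.4.1.1, repeated in SAP 7.1: "If 3 or more of the 10 treated subjects in cohort 1 experience a DLT by day 28, the guidance to the DLRT is" against starting cohort 2. The meeting serves "to determine if the safety profile of initial steps in cohort 1 is acceptable to begin enrollment of cohort 2", or to decide that the study should stop. SAP 3.3 refers to no other early stopping rule.

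The DLT window in 6.2.1 is the whole of cycle 1. Cohort 2's own gate is a DLT-free first 7 days in one sentinel subject (4.1).

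Other oversight continues:
- "Safety data will be reviewed on an ongoing basis" (9.4.1.1) and "Safety data will be continuously monitored throughout the whole treatment period" (4.1).
- "Sponsor in consultation with investigators may reconvene to make appropriate safety measures and adjustments as needed" (4.1).
- Under 6.2.1, any DLT stops that subject's dosing and is reviewed by investigator and sponsor, and each step increase needs sponsor approval.
- Sections 4.1 and 6.2.1 refer sentinel DLTs to the DLRT.
- Section 11.3 lets the sponsor stop the study for safety.

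On the threshold itself, protocol 4.1 and 6.2.1 and SAP 3.1 let cohort 2 go ahead when 3 or fewer of 10 cohort 1 subjects have had a DLT.

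**The concern.** The primary objective is the safety and tolerability of the combination. Section 2.3 expects AMG 330 toxicity soon after dose increases and more pembrolizumab events later in treatment. The day-28 count covers the first four of eight cohort 1 steps. The cohort 2 gate covers two of eight steps in one subject, and Section 4.3 calls CRS rare at those two doses (with AMG 330 alone). Cohort 2 also gives up the delayed start of pembrolizumab, which 2.3 names as a CRS mitigation, although dexamethasone, small steps and tocilizumab remain.

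If several DLTs occurred in these later periods, each would be reviewed, but whether new subjects keep starting would be decided case by case. A count fixed in advance would bring the same team together at the same point every time.

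The two versions of the day-28 threshold matter more directly. At exactly 3 of 10, one version lets cohort 2 proceed and the other advises against it.

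**Working it through.** **1. The plan's figures.** With X the number of DLTs in 10 subjects, P(X ≥ 3) at true rates of 10/20/30/40/50% is 0.070/0.322/0.617/0.833/0.945. This reproduces the stated 7/32/62/83/95%. The posterior is Beta(0.4 + x, 1.6 + 10 − x). P(rate > 20%) is 0.442 at x = 2 and 0.7195 at x = 3, so the > 70% criterion is first met at 3. Stopping only at 4 or more, which is what proceeding at 3 or fewer implies, would give 1/12/35/62/83%. The stated figures therefore belong to stopping at 3 or more.

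**2. What the count and gate cover (Tables 4-1 and 4-3).**
- Cohort 1: days 1-28 of 77. Not counted: 77 − 28 = 49 days (64%), the last four of eight steps, and the pembrolizumab doses on days 36 and 57.
- Cohort 2: the gate sees 7 of 56 infusion days (12.5%) and two of eight steps, in one subject. No later count exists, so the chance of a hold required by a count is 0% at every true rate.

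**3. Cohort 1 after day 28.** Let p be the cycle 1 DLT rate and s the share of DLTs occurring by day 28. The documents give no timing, so s is assumed. Then a = ps is the day-28 rate and q = (p − a)/(1 − a) is the later rate among subjects without an earlier DLT. The chance of passing day 28 with 2 or fewer of 10 and still reaching 3 or more in cycle 1 is the sum over k = 0, 1, 2 of Bin(k; 10, a) × P(Bin(10 − k, q) ≥ 3 − k):

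| Share by day 28 | p = 10% | 20% | 30% | 40% |
|---|---|---|---|---|
| three quarters | 4% | 14% | 22% | 22% |
| half | 6% | 25% | 44% | 51% |
| one quarter | 7% | 31% | 58% | 76% |

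**4. A third-DLT trigger in cohort 2.** Cohort 2's size is not stated: 6 evaluable is the minimum, and about 10 is 20 − 10. The chance of reaching a third DLT is P(Bin(n, p) ≥ 3):

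| n | p = 10% | 20% | 30% | 40% | 50% |
|---|---|---|---|---|---|
| 10 | 7% | 32% | 62% | 83% | 95% |
| 6 | 2% | 10% | 26% | 46% | 66% |

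Here p is the full-cycle rate. For scale, Section 4.3 reports DLTs in 6 subjects on monotherapy; if all 49 treated are the denominator, that is 6/49 = 12%.

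**5. A posterior-based count instead.** The day-28 criterion applied throughout would fire at 2 DLTs among 3-6 subjects (0.707 at 2/6) and 3 among 7-10. With 10 subjects it pauses in 13.5/42/70/87/96% at 10-50%. But it carries a 28-day criterion onto a 56-day window. Under an assumed constant hazard, a 10% day-28 rate becomes 1 − 0.9² = 19% over 56 days. At 19% this count pauses in 39% and the third-DLT trigger in 29%. Over cohort 1's 77 days the same rate becomes 1 − 0.9^(77/28) = 25%, and 3 or more of 10 then occurs in 48%.

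**6. Subjects spared.** This depends on enrolment spacing and DLT timing, neither of which is in the documents. In a simulation of the count in step 5 with weekly starts, 10 subjects and four assumed timings, the mean number spared is 0.2-0.9 at a 20% rate and 0.4-1.8 at 30%. The third-DLT trigger never fires earlier than that count, so it spares no more.

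**The case against.** The strongest reply is that oversight is already substantial, and that a fixed count in about 20 open-label subjects is a preference. Much of this stands.

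- The meeting is not limited to days 1-28. The other cohort 1 subjects start at least 21 days after the sentinel, so when the last completes day 28 the sentinel's schedule is at day 28 + 21 = 49 or later. Some later-step data will be seen.
- Any one of the four votes can withhold a recommendation to open cohort 2, whatever the count.
- Sentinel DLTs already go to the DLRT outside the scheduled meeting, so the single meeting is not a working cap.
- A posterior-based count has two weaknesses: the longer window (step 5), and the treatment of subjects early in cycle 1 as DLT-free. Two DLTs give a posterior of 0.907 among 3 treated but 0.636 among 7.

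A reader might infer that nobody watches safety after day 28, or that the day-28 count bears only on opening cohort 2. The documents support neither: monitoring continues throughout, and 9.4.1.1 gives stopping the study as an outcome of the meeting. A reader might also take the heading "Dose-cohort Study Escalation/De-escalation and Stopping Rules" in 6.2.1 as proof that a further rule was intended and left out. It can equally refer to the day-28 rule.

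What the reply does not supply is any number of later DLTs that requires a hold or a meeting. The provision for reconvening in 4.1 is permissive.

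**Conclusion.** The point holds in a limited form. After the scheduled day-28 meeting, neither document ties a number of DLTs across subjects to a hold on new starts or a DLRT meeting, in cohort 1 days 29-77 or in cohort 2 beyond its sentinel gate. This is a cheap safety improvement and not an absence of oversight.

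Its size depends on assumptions. In cohort 1, passing day 28 and then reaching 3 or more of 10 has probability 14-31% at a true rate of 20% and 22-58% at 30%, depending on the assumed share of DLTs by day 28. In cohort 2 the benefit is mainly a prompt, consistent review; few subjects are spared if starts are weekly.

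The threshold conflict needs no assumption. Allowing cohort 2 to proceed at 3 of 10 is wrong as written, because it contradicts the plan's own > 70% criterion and its stated stopping probabilities.

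**What to change.** In protocol 9.4.1.1 and 11.3 and SAP 7.1:

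- Provide for at least one DLRM in place of exactly one.
- In cohort 2, hold new starts and reconvene the existing DLRT at a simple prespecified count, such as the third cycle 1 DLT. In cohort 1, reconvene it if cumulative cycle 1 DLTs reach 3 of 10.
- If a posterior-based count is preferred, state the acceptable DLT rate for the full cycle 1 window instead of reusing the day-28 20% criterion, say how subjects still in cycle 1 are counted, and report the operating characteristics.

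Separately, in protocol 4.1 and 6.2.1 and SAP 3.1, change the condition for proceeding from 3 or fewer to 2 or fewer of 10.

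The cost is wording, occasional ad hoc meetings of an existing team and short enrolment holds. The third-DLT trigger calls a cohort 2 review in 7% (10 subjects) or 2% (6 subjects) at a true full-cycle rate of 10%, and in 32% or 10% at 20%. The cohort 1 trigger adds a meeting in 4-7% at 10% and 14-31% at 20%. With 6 subjects the third-DLT trigger is not very sensitive (26% at a 30% rate). A hold may take a subject past the 14-day screening window, but Section 5.4 allows rescreening up to 3 times. A hold leads to review, not to termination.

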1. SITE INFORMATION							
Site Number	Investigator			Country			
Reporter	Phone Number ()	Fax Number ()					
2. SUBJECT INFORMATION							
Subject ID Number	Age at event onset			Sex  F  M	Race	If applicable, provide End of Study date	
If this is a follow-up to an event reported in the EDC system (eg, Rave), provide the adverse event term: _____ and start date: Day ____ Month ____ Year ____							
3. SERIOUS ADVERSE EVENT							
Provide the date the Investigator became aware of this information: Day Month Year				Check only if event occurred before first dose of IP	Is event serious?  Serious  Fatal  Life-threatening  Required/prolonged hospitalization  Persistent or significant disability/incapacity	Relationship Is there a reasonable possibility that the Event may have been caused by IP or an Amgen device used to administer the IP?	Outcome of Event -Resolved -Not resolved -Fatal -Unknown -eq, biopsy
Serious Adverse Event diagnosis or syndrome If diagnosis is unknown, enter signs / symptoms and provide diagnosis, when known, in a follow-up report List one event per line. If event is fatal, enter the cause of death. Entry of "death" is not acceptable, as this is an outcome.							
Date Started Day Month Year	Date Ended Day Month Year	AMG 330 Now  Yes  No  Yes	Pembrolizumab Now  Yes  No  Yes				
Serious Criteria: 01 Fatal 02 Immediately life-threatening	03 Required/prolonged hospitalization 04 Persistent or significant disability /incapacity				05 Congenital anomaly / birth defect 06 Other medically important serious event		
4. Was subject hospitalized or was a hospitalization prolonged due to this event?  No  Yes If yes, please complete all of Section 4							
Date Admitted Day Month Year				Date Discharged Day Month Year			
5. Was IP/drug under study administered/taken prior to this event?  No  Yes If yes, please complete all of Section 5							
IP/Amgen Device: Amgen IP/IMP: AMG 330		Date of Initial Dose Day Month Year	Prior to, or at time of Event Date of Dose Dose Route Frequency		Action Taken with Product 01 Still being Administered 02 Permanently discontinued 03 Withheld	Lot # and Serial #  Unknown  Serial #  Unavailable / Unknown	
Non-Amgen IP/IMP: Pembrolizumab		 Open Label				Lot #  Unknown  Serial #  Unavailable / Unknown	

Approved

A Study # 20170646 AMG 330	Electronic Serious Adverse Event Contingency Report Form For Restricted Use												
		Site Number			Subject ID Number								
6. CONCOMITANT MEDICATIONS (eg, chemotherapy) Any Medications?  No  Yes If yes, please complete:													
Medication Name(s)		Start Date Day Month Year	Stop Date Day Month Year	Co-suspect  Yes  Yes	Continuing  Yes  Yes	Dose	Route	Freq.	Treatment Med  Yes  Yes				
7. RELEVANT MEDICAL HISTORY (include dates, allergies and any relevant prior therapy)													
8. RELEVANT LABORATORY VALUES (include baseline values) Any Relevant Laboratory values?  No  Yes If yes, please complete:													
Date Day Month Year	Test												
	Unit												
9. OTHER RELEVANT TESTS (diagnostics and procedures) Any Other Relevant tests?  No  Yes If yes, please complete:													
Date Day Month Year	Additional Tests				Results				Units				

Approved

Approved

11.5 Appendix 5. Contraceptive Guidance and Collection of Pregnancy and Lactation Information

Study-specific contraception requirements for male and female subjects of childbearing potential are outlined in [Sections 5.1](#) and [5.2](#).

Male and female subjects of childbearing potential must receive pregnancy prevention counseling and be advised of the risk to the fetus if they become pregnant or father a child during treatment and for 120 days after the last dose of protocol-required therapies.

Additional medications given during the study may alter the contraceptive requirements. These additional medications may require female subjects to use highly effective methods of contraception and/or for an increased length of time. In addition, male subjects may also be required to use contraception. The investigator must discuss these contraceptive changes with the subject.

Definition of Females of Childbearing Potential

A female is considered fertile following menarche and until becoming post-menopausal unless permanently sterile. Permanent sterilization methods include hysterectomy, bilateral salpingectomy, and bilateral oophorectomy.

Females in the following categories are not considered female of childbearing potential:

- Premenopausal female with 1 of the following:
 - Documented hysterectomy;
 - Documented bilateral salpingectomy; or
 - Documented bilateral oophorectomy.
- Premenarchal female
- Postmenopausal female
 - A postmenopausal state is defined as no menses for 12 months without an alternative medical cause. A high follicle stimulating hormone level in the postmenopausal range may be used to confirm a postmenopausal state in women not using hormonal contraception or hormonal replacement therapy (HRT). However, in the absence of 12 months of amenorrhea, a single follicle stimulating hormone measurement is insufficient.
 - Females on HRT and whose menopausal status is in doubt will be required to use 1 of the non-hormonal highly effective contraception methods if they wish to continue their HRT during the study. Otherwise, they must discontinue HRT to allow confirmation of postmenopausal status before study enrollment

Contraception Methods for Female Subjects

Highly Effective Contraceptive Methods

Note: Failure rate of < 1% per year when used consistently and correctly.

- Combined (estrogen and progestogen containing) hormonal contraception associated with inhibition of ovulation (oral, intravaginal, or transdermal)
- Progestogen-only hormonal contraception associated with inhibition of ovulation (oral, injectable, implantable)
- Intrauterine device (IUD)
- Intrauterine hormonal-releasing system
- Bilateral tubal ligation/occlusion
- Vasectomized partner (provided that partner is the sole sexual partner of the female subject of childbearing potential and that the vasectomized partner has received medical assessment of the surgical success)
- Sexual abstinence (defined as refraining from heterosexual intercourse during the entire period of risk associated with the study treatments; the reliability of sexual abstinence must be evaluated in relation to the duration of the study and the preferred and usual lifestyle of the subject)

Contraception Methods for Male Subjects

- Sexual abstinence (defined as refraining from heterosexual intercourse during the entire period of risk associated with protocol-required therapies; the reliability of sexual abstinence must be evaluated in relation to the duration of the study and the preferred and usual lifestyle of the subject)
- Use a condom during treatment and for an additional 120 days after the last dose of protocol-required therapies

The female partner should consider using an acceptable method of effective contraception such as: hormonal, IUD, intrauterine hormonal-releasing system, female barrier method (diaphragm, cap, sponge [a female condom is not an option because there is a risk of tearing when both partners use a condom]).

Note: If the male's sole female partner is of non-childbearing potential or has had a bilateral tubal ligation/occlusion, he is not required to use additional forms of contraception during the study.

Unacceptable Methods of Birth Control for Male and Female Subjects

Birth control methods that are considered unacceptable in clinical trials include:

- Periodic abstinence (calendar, symptothermal, post-ovulation methods)
- Withdrawal (coitus interruptus)
- Spermicides only
- Lactational amenorrhea method

Collection of Pregnancy Information

Female Subjects Who Become Pregnant

- Investigator will collect pregnancy information on any female subject who becomes pregnant while taking protocol-required therapies through 120 days after the last dose of study drug.
- Information will be recorded on the Pregnancy Notification Form (see [Figure 11-2](#)). The form must be submitted to Amgen Global Patient Safety within 24 hours of learning of a subject's pregnancy. (Note: Sites are not required to provide any information on the Pregnancy Notification Form that violates the country or regions local privacy laws).
- After obtaining the female subject's signed authorization for release of pregnancy and infant health information, the investigator will collect pregnancy and infant health information and complete the pregnancy questionnaire for any female subject who becomes pregnant while taking protocol-required therapies through 120 days after the last dose of the study drug. This information will be forwarded to Amgen Global Patient Safety. Generally, infant follow-up will be conducted up to 12 months after the birth of the child (if applicable).
- Any termination of pregnancy will be reported to Amgen Global Patient Safety, regardless of fetal status (presence or absence of anomalies) or indication for procedure.
- While pregnancy itself is not considered to be an adverse event or serious adverse event, any pregnancy complication or report of a congenital anomaly or developmental delay, fetal death, or suspected adverse reactions in the neonate will be reported as an adverse event or serious adverse event. Note that an elective termination with no information on a fetal congenital malformation or maternal complication is generally not considered an adverse event, but still must be reported to Amgen as a pregnancy exposure case.
- If the outcome of the pregnancy meets a criterion for immediate classification as a serious adverse event (eg, female subject experiences a spontaneous abortion, stillbirth, or neonatal death or there is a fetal or neonatal congenital anomaly) the investigator will report the event as a serious adverse event.
- Any serious adverse event occurring as a result of a post-study pregnancy which is considered reasonably related to the study treatment by the investigator, will be reported to Amgen Global Patient Safety as described in [Section 11.4](#). While the investigator is not obligated to actively seek this information in former study subjects, he or she may learn of a serious adverse event through spontaneous reporting.
- Any female subject who becomes pregnant while participating will discontinue study treatment (see [Section 7.1](#) for details).

Male Subjects With Partners Who Become Pregnant or Were Pregnant at the Time of Enrollment

- In the event a male subject fathers a child during treatment, and for an additional 120 days after discontinuing protocol-required therapies, the information will be recorded on the Pregnancy Notification Form. The form (see [Figure 11-2](#)) must be submitted to Amgen Global Patient Safety within 24 hours of the site's awareness of the pregnancy. (Note: Sites are not required to provide any information on the Pregnancy Notification Form that violates the country or regions local privacy laws).

- The investigator will attempt to obtain a signed authorization for release of pregnancy and infant health information directly from the pregnant female partner to obtain additional pregnancy information.
- After obtaining the female partner's signed authorization for release of pregnancy and infant health information, the investigator will collect pregnancy outcome and infant health information on the pregnant partner and her baby and complete the pregnancy questionnaires. This information will be forwarded to Amgen Global Patient Safety.
- Generally, infant follow-up will be conducted up to 12 months after the birth of the child (if applicable).
- Any termination of the pregnancy will be reported to Amgen Global Patient Safety regardless of fetal status (presence or absence of anomalies) or indication for procedure.

Collection of Lactation Information

- Investigator will collect lactation information on any female subject who breastfeeds while taking protocol-required therapies through 120 days after the last dose of study drug.
- Information will be recorded on the Lactation Notification Form ([Figure 11-2](#)) and submitted to Amgen Global Patient Safety within 24 hours of the investigator's knowledge of event.
- Study treatment will be discontinued if female subject breastfeeds during the study as described in [exclusion criterion 229](#).
- With the female subjects signed authorization for release of mother and infant health information, the investigator will collect mother and infant health information and complete the lactation questionnaire on any female subject who breastfeeds while taking protocol-required therapies through 120 days after discontinuing protocol-required therapies.

Approved

Figure 11-2. Pregnancy and Lactation Notification Forms

Amgen Proprietary - Confidential

AMGEN® Pregnancy Notification Form

Report to Amgen at: USTO [contact], Non-US [contact] or email (worldwide): [contact]

1. Case Administrative Information

Protocol/Study Number: 20170646Study Design: Interventional Observational (If Observational: Prospective Retrospective)

2. Contact Information

Investigator Name _____ Site # _____

Phone (____) _____ Fax (____) _____ Email _____

Institution _____

Address _____

3. Subject Information

Subject ID # _____ Subject Gender: Female Male Subject age (at onset): _____ (in years)

4. Amgen Product Exposure

Amgen Product	Dose at time of conception	Frequency	Route	Start Date
AMG 330				mm____/dd____/yyyy____

Was the Amgen product (or study drug) discontinued? Yes No

If yes, provide product (or study drug) stop date: mm____/dd____/yyyy____

Did the subject withdraw from the study? Yes No

5. Pregnancy Information

Pregnant female's last menstrual period (LMP) mm____/dd____/yyyy____ Unknown N/A

Estimated date of delivery mm____/dd____/yyyy____

If N/A, date of termination (actual or planned) mm____/dd____/yyyy____

Has the pregnant female already delivered? Yes No Unknown N/A

If yes, provide date of delivery: mm____/dd____/yyyy____

Was the infant healthy? Yes No Unknown N/A

If any Adverse Event was experienced by the infant, provide brief details: _____

Form Completed by:

Print Name: _____ Title: _____

Signature: _____ Date: _____

Approved

Amgen Proprietary - Confidential

AMGEN® Lactation Notification FormReport to Amgen at: USTO [contact], Non-US [contact] or email (worldwide): [contact]**1. Case Administrative Information**

Protocol/Study Number: 20170646

Study Design: Interventional Observational (If Observational: Prospective Retrospective)**2. Contact Information**

Investigator Name _____ Site # _____

Phone (____) _____ Fax (____) _____ Email _____

Institution _____

Address _____

3. Subject Information

Subject ID # _____ Subject age (at onset): _____ (in years)

4. Amgen Product Exposure

Amgen Product	Dose at time of breast feeding	Frequency	Route	Start Date
AMG 330				mm ____/dd ____/yyyy ____

Was the Amgen product (or study drug) discontinued? Yes No

If yes, provide product (or study drug) stop date: mm ____/dd ____/yyyy ____

Did the subject withdraw from the study? Yes No**5. Breast Feeding Information**Did the mother breastfeed or provide the infant with pumped breast milk while actively taking an Amgen product? Yes No

If No, provide stop date: mm ____/dd ____/yyyy ____

Infant date of birth: mm ____/dd ____/yyyy ____

Infant gender: Female MaleIs the infant healthy? Yes No Unknown N/AIf any Adverse Event was experienced by the mother or the infant, provide brief details: _____

_____**Form Completed by:**

Print Name: _____ Title: _____

Signature: _____ Date: _____

Approved

